3.1.2.1 Maximum Tolerated Dose 1 (MTD1)

Dose escalation will proceed using 2 parts, single subject cohorts and multiple subject cohorts. In the single subject cohorts, single subjects will be enrolled at initial dose levels. When any pharmacologic activity (including, but not limited to, infusion reactions, cytokine release syndrome, decrease in peripheral blood blasts, or decrease in white blood cell count) is observed, the cohort size will be increased to multiple subject cohorts (N = 2 to 4 subjects). When the initial dose-limiting toxicity (DLT) is observed, the BLRM design will be used to guide dose level selection. After each cohort, the model's recommended MTD dose level for evaluation is the dose level with the highest probability of the target TPI, but with a less than 0.25 probability of an excessive or unacceptable TPI. The actual dose selected at each dose decision may be at or below the model's recommended dose as recommended by the DLRT after considering all information.

The dose escalation will be stopped when any of the following occurs:

- A minimum of 6 subjects have been treated at the MTD1 level
- When the sample size reaches 120 subjects
- Or as recommended by the DLRT after considering available safety, PK, PD, and efficacy data

[figure not shown]

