3.1.3 Expansion Cohort

At completion of the dose escalation cohorts, approximately 90 additional subjects (approximately 40 R/R AML subjects in the FIH cohorts and 50 MRD+ AML subjects in the MRD+ cohorts) will be enrolled in dose expansion cohorts to gain further clinical experience, safety, and efficacy data in subjects with AMG 427. The dose to be evaluated will be at or below the MTD estimated in the dose escalation cohorts. Once the preliminary MTD and R2PD are established, the FDA will be provided with brief interim results of the dose escalation phase.

In the expansion phase, all available study data will be reviewed (with recruitment ongoing) by the DLRT once every 6th subject has at least completed their first treatment cycle plus 2 weeks or dropped out of treatment/study, whichever occurs earlier. The MTD will be further evaluated by applying BLRM using all available data, including data from subjects in the expansion phase. Ad hoc meetings may be convened any time in case of important safety events (see also Section 6.2.1.3).

Based on emerging safety data, the planned dose level and dose schedule may be modified during the conduct of the expansion phase. Additionally, enrollment to dose expansion will be paused and possibly terminated if safety stopping rules and/or efficacy futility rules are met (see Section 10.3 for details).

A final estimate of the MTD and RP2D using BLRM will be evaluated and confirmed utilizing all DLT-evaluable subjects from the dose escalation and the dose expansion cohorts. For definition of DLT-evaluable, see Section 6.2.1.3. Additional expansion cohorts testing alternative dose levels or biologic subsets may be considered by amendment.

The overall study design is described by a [Study Design and Treatment Schema](#) at the end of the protocol synopsis section.

The study endpoints are defined in Section 10.1.1.

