10.3 Adaptive Design

During dose expansion, Amgen will conduct evaluations of the ongoing DLT event rate and the ongoing overall response rate.

Safety Stopping Rules during Dose Expansion:

During dose expansion, Amgen will conduct evaluations of the ongoing DLT event rate to assess if the threshold for pausing enrollment has been reached. If these stopping rules are met, then enrollment to the dose expansion will be paused pending a review of safety data and available pharmacokinetic, pharmacodynamics, and efficacy data by the DLRT. This review may result in early termination of the study, notification to Health Authorities, or may result in re-initiation of enrollment. The DLRT may implement additional measures, as appropriate, to reduce the risk of toxicity or to adapt and manage the toxicity. The stopping rules to pause enrollment use a Bayesian approach proposed by [Thall, et al \(1995\)](#); enrollment to dose expansion will be halted if the posterior probability that the **DLT** rate is greater than 20% is $> 80\%$. The stopping boundaries assuming a prior distribution of Beta (0.40, 1.60) are presented in [Table 26](#) and the operating characteristics with pre-specified batch size of 6 new subjects per batch are presented in [Table 35](#). The evaluations could occur more frequently if necessary to address emerging safety concerns.

Table 26. Stopping Boundary for Dose Expansion With Posterior Probability of 80% DLT Limit of 20%

Number of subjects	Pause study enrollment if observing the number of these many DLT events
6	≥ 3
12	≥ 4
18	≥ 6
24	≥ 7
30	≥ 9
36	≥ 10
40	R/R AML expansion cohort completes
42	≥ 11
48	≥ 13
50	MRD+ AML expansion cohort completes

AML = acute myeloid leukemia, MRD+ = minimal/measurable residual disease-positive,
 R/R = relapsed/refractory.

Table 27. Operating Characteristics With Batch Size of 6 Subjects

True DLT rate	R/R AML		MRD+ AML	
	Probability of early stopping of dose expansion	Average dose expansion sample size*	Probability of early stopping of dose expansion	Average dose expansion sample size*
0.10	3.8%	38.9	3.9%	48.5
0.20	34.0%	31.5	37.8%	37.8
0.25	58.2%	25.6	64.9%	29.4
0.30	78.9%	19.9	85.5%	21.6
0.35	91.6%	15.4	95.7%	16.0
0.40	97.4%	12.2	99.1%	12.3
0.50	99.9%	8.7	100%	8.7

AML = acute myeloid leukemia, MRD+ = minimal/measurable residual disease-positive,
 R/R = relapsed/refractory.

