10.4.1 Interim Analyses and Early Stopping Guidelines

Safety data will be reviewed on an ongoing basis. Based on accumulating toxicity information, BLRM will be used to make dosing recommendations. In DLRMs, Amgen, in consultation with the site investigators, will review the BLRM recommended dose level and will review all available cumulative data by cohort prior to making dose escalation decisions. As a sensitivity analysis, a 1-parameter Continual Reassessment Method (CRM) model may be used to estimate the dose-toxicity relationship to help making dose escalation decisions. Adverse events and DLTs observed in all subjects will be evaluated continually and fully integrated into all DLRMs and considered in all enrollment and dosing decisions.

Ad-hoc interim analysis for efficacy parameters will be conducted after dose escalation is completed. Once preliminary MTD and R2PD is established, FDA will be provided with brief interim results of the dose escalation phase.

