Appendix H. Two-Parameter BLRM Design

A 2-parameter Bayesian logistic regression model (BLRM, Neuenschwander et al, 2008) is used to guide dose escalation. The MTD target Toxicity Probability Interval (TPI) for DLT is (0.20, 0.33) and TPIs of (0.33, 0.60) and (0.60, 1.00) are defined as excessive and unacceptable, respectively. The design seeks to identify a dose most likely to have a DLT rate in the target TPI, but with overdose control that limits the possibility the dose has an excessive or unacceptable DLT rate (Babb et al, 1998). The probability of a DLT at dose level d_i is assumed to follow a Bernoulli distribution with probability p_i where the logit of p_i increases linearly with the log of the standardized dose in the following 2-parameter logistic model:

$$\log [p_i/(1-p_i)] = \text{logit}(p_i) = \log[a] + \exp(\log[b]) \log (d_i/d_{\text{ref}})$$

where a and b are random variables and d_{ref} is 1 of the planned dose selected as the reference dose.

A bi-variate normal prior distribution (Neuenschwander et al, 2008) was selected for $\theta = (\log a, \log b)$ where the probability that the true DLT rate is ≤ 0.40 at $\blacksquare \mu\text{g}$ is 0.90 and the probability the true DLT rate is ≤ 0.05 at the reference dose ($\blacksquare \mu\text{g}$) is 0.05. Additionally, the prior is such that p_i is approximately 0.05 for the $\blacksquare \mu\text{g}$ dose and 0.25 for the reference dose. Once the $\blacksquare \mu\text{g}$ is deemed safe by Dose Level Review Team (DLRT), the reference dose will be updated to the highest planned dose level.

The operating characteristics of the 2-parameter BLRM design were evaluated via simulation. The cohort size was fixed to 2 or 4 subjects. All simulated studies start with the multiple subject cohorts. The initial multiple subject dose level is $\blacksquare \mu\text{g}$ and subsequent doses were selected based on the following rules:

- After each cohort, the next dose is the one with the highest probability of the target TPI, but with a less than 0.25 probability of an excessive or unacceptable TPI.
- Skipping dose levels is not allowed.

Dose escalation was stopped given 1 or more of the following conditions:

- There have been at least 6 subjects treated at the dose recommended by the model.
- A maximum number of 36 subjects in the multiple subject cohorts is evaluated (note: this assumes that $n = 4$ subjects treated in single subject cohorts).

Operating characteristics are described below.

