Operating characteristics

A total of [REDACTED] dose levels (unit: μg) were considered: [REDACTED] and [REDACTED] in these simulations of the multiple subject cohorts.

The design was evaluated for 3 possible dose-response scenarios: “Low,” “Mid,” and “High” MTD. [Table 30](#) shows the dose level and true probability of DLT for each scenario used in the simulated studies estimating the MTD. [Table 31](#) reports the operating characteristics from 10 000 simulated studies estimating the MTD when the target TPI is (0.20, 0.33). The rate of MTD selected and the number of subjects assigned to each dose level are presented in [Table 32](#).

[figure not shown]
[figure not shown]

Table 31. Operating Characteristics by Scenario for Simulated Studies Estimating the MTD When the Target TPI is (0.20, 0.33)

[figure not shown]
MTD Scenario	High		Mid		Low	
	4 subjects per cohort	2 subjects per cohort	4 subjects per cohort	2 subjects per cohort	4 subjects per cohort	2 subjects per cohort
Number of Subjects	24	14	20	14	16	10
Median (IQR)	(20 to 32)	(12 to 16)	(16 to 28)	(8 to 16)	(8 to 20)	(6 to 16)
Number of DLTs	3	2	4	2	6	4
Median (IQR)	(2 to 5)	(1 to 3)	(3 to 5)	(1 to 3)	(5 to 7)	(3 to 5)
Proportion of DLT (%)	14	14	20	21	40	42
Median (IQR)	(10 to 19)	(7 to 21)	(16 to 25)	(17 to 40)	(31 to 50)	(30 to 50)
Percentage of studies recommending dose with DLT probability of:						
≤ 10%	3.3%	24.7%	2.8%	13.8%	0.9%	9.0%
> 10% and ≤ 20%	31.8%	42.0%	26.7%	37.5%	25.0%	35.7%
> 20% and ≤ 33%	64.9%	33.3%	70.5%	48.7%	74.1%	55.3%
> 33%	0%	0%	0%	0%	0%	0%
Probability of identifying MTD to have 15% to 33% DLT probability	86.7%	60.6%	88.8%	76.1%	94.6%	82.7%

[figure not shown]
DLT = dose-limiting toxicity; IQR = interquartile range; MTD = maximum tolerated dose; TPI = toxicity probability interval.

[figure not shown]

Extremely Toxic Case

In addition, the performance of BLRM under the extremely toxic scenario was evaluated through simulations, where the DLT rate is expected to be high (the DLT rate exceeds 0.33 at all the tested dose levels) as shown in [Table 33](#). In this extremely toxic scenario, it is highly likely to have a Grade ≥ 2 treatment-related adverse event or DLT observed at the initial dose levels. Therefore, simulation results are presented in [Table 34](#) and [Table 35](#) by the dose level for initiation of the multiple subject cohorts.

Operating Characteristics for Standard 3+3 Design

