## 9.6 Safety Analyses

### 9.6.1 Analyses of Primary Safety Endpoint(s)

Subject incidence of DLTs will be used to fit the BLRM model to estimate the probability of having a DLT across dose levels at DLRM. Separate BLRM analysis will be conducted for each dose regimen, eg, MTD1 and MTD2 if there is one dose step. The BLRM analysis will be performed based on the Section 9.1 in Statistical Analysis Plan. Summary of the subject incidence of DLT will be provided.

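### Does moving the BLRM reference dose, without saying what happens to the prior set there, weaken the 0.25 overdose limit?

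*Protocol*

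**What the plan says.** Appendix H models the log-odds of a DLT as log a + b·log(d/d_ref), where d_ref "is 1 of the planned dose selected as the reference dose". The bivariate normal prior is described by two statements at a lower (redacted) dose and two at the reference dose: a rate of about 0.25, and probability 0.05 that the rate is at most 0.05. The same paragraph then says that, after a Dose Level Review Team (DLRT) safety judgement, "the reference dose will be updated to the highest planned dose level". SAP 9.1 repeats this and refers back to Appendix H.

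The recommended dose has the highest probability of the target interval, "but with a less than 0.25 probability of an excessive or unacceptable TPI" (Protocol 3.1.2.1). SAP 9.6.1 adds: "Separate BLRM analysis will be conducted for each dose regimen, eg, MTD1 and MTD2 if there is one dose step". Protocol 10.4.1 says: "Based on accumulating toxicity information, BLRM will be used to make dosing recommendations". For the later phase, Protocol 3.1.3 says: "The MTD will be further evaluated by applying BLRM using all available data, including data from subjects in the expansion phase".

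**The concern.** The prior is tied to the reference dose, and the reference dose moves. The text does not say what happens to the prior at that moment. Only dose values are blacked out in these sentences, so redaction does not explain the silence.

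Since b is positive, keeping the same (log a, log b) numbers with a larger d_ref lowers the prior DLT rate at every dose. Refitting the anchors at the new reference dose lowers it at every dose above the lower anchor. The trigger is a safety judgement on data that stay in the same regimen's likelihood, so favourable data could count twice. The limit P(DLT rate > 0.33) < 0.25 governs escalation and is part of the MTD definition. Passing it on less evidence would matter most at the next dose up, where few or no subjects have been treated. A separate fit per regimen gives each prior more weight.

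**Working it through.** **Inputs.** The model, the anchors and the 0.25 limit come from Appendix H and Protocol 3.1.2. The doses are redacted; the slope prior and the correlation are not given. They are assumed below.

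**Prior at the reference dose.** Take 0.25 as the median.
- Mean of log a = logit(0.25) = -1.099.
- SD = (logit 0.25 - logit 0.05)/1.645 = (-1.099 + 2.944)/1.645 = 1.122.
- logit(0.33) = -0.708, so z = (-0.708 + 1.099)/1.122 = 0.348 and P(rate > 0.33) = 0.364.

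A prior meeting all four stated anchors exists, so the description is coherent. Before data, the reference dose fails the 0.25 limit.

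**Three ways to move d_ref.**
1. Transform: log a_new = log a + b·log(d_new/d_old). Then log a_new + b·log(d/d_new) = log a + b·log(d/d_old). The curve is identical and the 0.364 stays. The update is only a relabelling.
2. Carry the same numbers over: the 0.364 at the old reference dose becomes 0.14-0.31.
3. Refit the four anchors at the new reference dose: it becomes 0.17-0.31.

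The ranges in 2 and 3 use all four anchors, correlation 0 and -0.5, and f from 0.1 to 1.0. Here f is the log distance from old to new reference dose, divided by the log distance from the lower anchor dose to the old reference dose.

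**After data, assumed slopes.** Data: 1/6 DLTs at the old reference dose and 0/4 at each of 1/2, 1/4, 1/8 and 1/16 of it. The median slope is 1.00, 0.80, 0.54 or 0.40, with log a and log b independent. P(rate > 0.33) at 1.5 times the old reference dose:
- Original prior: 0.251, 0.180, 0.091, 0.049 with SD(log b) = 0.5; 0.439, 0.375, 0.273, 0.202 with SD(log b) = 1.
- Carried over: 0.037-0.240 with d_ref x1.5, 0.029-0.116 with x2, 0.020-0.050 with x3.

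Three of the 8 settings (0.439, 0.375, 0.273) go from failing to passing, and one (0.251) sits on the limit. With correlation -0.5 it is 2 of 8, with +0.5 it is 3 of 8, and with no lower-dose data 7 of 8. After 0/6 with independence no decision changes. With correlation +0.5 and a 1.5-fold move the posterior rises in some settings, for example from 0.188 to 0.200.

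**After data, all four anchors enforced (f = 0.25).** With 1/4 at the old reference dose, P(rate > 0.33) there goes from 0.29 to 0.23-0.25. With 0/4 at a middle dose and 1/6 at the old reference dose, it goes from 0.49-0.57 to 0.17-0.22 at the new top dose.

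**What the update buys.** With the prior frozen and f = 0.25-0.5, more than 60 DLT-free subjects at the old reference dose would be needed before the top dose passed. After the update it is 2-5.

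**Simulated trials on an assumed dose grid, cohorts of 4:**

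| Outcome | Prior fixed | Carried over, x2 | Carried over, x3 |
|---|---|---|---|
| Selects rate > 0.33; true rates 0.20 and 0.40 at 1x and 1.5x | 6-24% | 26-37% | 31-41% |
| Selects rate > 0.33; true rates 0.15, 0.28, 0.42 at 1x, 1.5x, 2x | 4-20% | 12-26% | 27-33% |
| Selects target, same rates as the row above | 13-35% | 37-42% | 35-36% |
| Selects target, no dose above 0.33 | 21-64% | 18-69% | 41-76% |

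The first scenario has no dose inside (0.20, 0.33), which favours an overdose result. More overdose selection comes with more target selection in the third row and, at x3, in the fourth; at x2 the fourth row is mixed.

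**The case for a change.** The strongest case for a change is this. The rule is missing, and it bears on the main escalation control. Two statisticians could hand the DLRT different recommendations from identical data. The study has already had a fatal cytokine release event and a partial clinical hold, and a sentence in each document would settle the matter. Enforcing the stated anchors does not remove the effect.

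The silence stands, and so does the general direction of the prior shift. Three parts of the case do not carry through to a change.

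First, the proposed sentence is not neutral. Fixing the curve makes a stated update do nothing. The anchors are worded as properties of the reference dose, so a natural reading is that they move with it. A transformed log a is a normal plus a multiple of the lognormal b, so the new pair would no longer be bivariate normal. Insisting on an unchanged prior is a preference for caution over escalation, on which reasonable statisticians differ.

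Second, the figures are not the plan's. If the 0.40/0.90 and 0.05 anchors share a dose and log a and log b are independent, SD(log b) of 0.5 or 1 gives 0.97 or 0.95 in place of 0.90; about 3 is needed. The fixed-prior simulations select an overdose in 4-24% of trials, while Table 31 reports 0% in all six columns. Appendix H says "The design was evaluated for 3 possible dose-response scenarios", but the tables with their true rates are not shown. Whether the switch was simulated is therefore a question, not a demonstrated fault.

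Third, other controls remain:
- The DLRT may choose a lower dose (3.1.2.1), there is a 7-day gap after the first subject in a cohort (3.1.2.2), and at least 6 subjects are required at the MTD (3.1.2).
- DLTs after the window enter the BLRM (3.1.2.2).
- A one-parameter CRM may be run as a sensitivity analysis (10.4.1), and all grade 3 or higher toxicities are reviewed (10.4.2).
- The expansion pause rule has its own prior: "The stopping boundaries assuming a prior distribution of Beta (0.40, 1.60) are presented in" Table 26 (10.3).

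None of these tells the DLRT which prior was used, but each limits what a more permissive one could do. Section 3.1.2.1 also has the BLRM guide selection once a first DLT is seen, so comparisons without data carry little weight (5.1 reads differently).

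**Conclusion.** No change to the plan follows. Both documents leave out how the prior is treated when d_ref moves, but the limit itself does not change and the update is stated openly. If the analyst preserves the curve, the effect is zero. If the prior is carried over or refitted, the limit may be met on less evidence: 3 of 8 assumed settings change after 1/6 DLTs with lower-dose data, and none after 0/6 with independent parameters. The effect is not negligible under every assumption. With all four anchors enforced, some decisions also change.

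The size for this trial cannot be determined, because it depends on redacted doses and on a slope prior and correlation that are not given. For a small move with positive correlation even the direction of the posterior is uncertain. What is left is a trade-off between overdose control and reaching the target interval, plus hyperparameters that must be fixed to run the model at all. The DLRT includes the biostatistician (10.4.2), who can say which prior produced a recommendation. The final MTD draws on all DLT-evaluable escalation and expansion subjects (3.1.3), where the prior should count for less.

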Appendix I. Protocol-specific Anticipated Serious Adverse Events

Anticipated serious adverse events are events that are anticipated to occur in the study population at some frequency independent of investigational product exposure and do not need to be reported individually as an FDA IND safety report by the sponsor. Identification and reporting of anticipated serious adverse events is the responsibility of the sponsor; the investigator is responsible for reporting adverse events and serious adverse events as described in Section 9.

Anticipated Serious Adverse Events for Study 20170528

Cancer Pain
Metastasis
Acute Myeloid Leukaemia

¹ MedDRA Version 24.0

Amendment 7

Protocol Title: A Phase 1 First-in-human Study Evaluating the Safety, Tolerability, Pharmacokinetics, Pharmacodynamics and Efficacy of AMG 427 in Subjects With Acute Myeloid Leukemia

Amgen Protocol Number (AMG 427) 20170528

IND number BB-IND 138440

NCT Number: NCT03541369

Eudra CT: 2018-001389-40

Amendment Date: 16 March 2022

Rationale:

This protocol is being amended to include additional risk mitigation measures for cytokine release syndrome (CRS). Changes related to enhanced CRS risk mitigation were mandated by the United States Food and Drug Administration (FDA) in a Partial Clinical Hold letter dated 19 July 2021 that resulted from the observation of a fatal event of grade 5 CRS observed in the study. Additionally, changes to the protocol include those requested by FDA and agreed upon by Amgen during the 30-day review period of Amgen's Complete Response submission dated 12 October 2021 (SN 0045).

The following changes were made to the protocol:

- Changes in risk mitigation measures by CRS grades to enhance patient monitoring
- Updated dose modification criteria to adapt the dosing strategy when events of CRS occur
- Changed the safety stopping rule during expansion based on grade 4 and above adverse events to a stopping rule based on dose-limiting toxicity (DLT) rate, to allow safety stopping due to grade 2 and 3 CRS events which qualify as DLT and to prevent excess stopping due to non-treatment related grade 4 events
- Additional pharmacologic interventions were added to the protocol to ensure prompt treatment of CRS when it does occur
- Adjustment of dosing strategy upon study restart (eIV infusion and lowered target doses)

- Added exclusion criterion and table related to severe acute respiratory syndrome coronavirus 2 (SARS-CoV-2)
- Revised tables and language to reflect update to American Society for Transplantation and Cellular Therapy (ASTCT) Consensus Grading criteria for CRS and immune-effector associated neurotoxicity syndrome (ICANS)
- Added language in other protocol required therapies to include methylprednisone, siltuximab, and anakinra, and updated dose modification criteria regarding treatment interruption and re-start in case of adverse events during the infusion treatment interruption and re-start in case of adverse events during the infusion
- Added stopping rule for siltuximab dosing
- Globally, removed subcutaneous AMG 427 dosing cohorts from the study

Amendment 6

Title: A Phase 1 First-in-human Study Evaluating the Safety, Tolerability, Pharmacokinetics, Pharmacodynamics and Efficacy of AMG 427 in Subjects With Acute Myeloid Leukemia

AMG 427

Amgen Protocol Number 20170528

IND number BB-IND 138440

Amendment Date: 24 March 2021

Rationale:

This protocol is being amended to allow for the enrollment of acute myeloid AML subjects with minimal/measurable residual disease (MRD).

The following changes were made to the original protocol, dated 22 March 2018:

- References to “Relapsed/Refractory” in the protocol title and in relevant sections of the protocol were removed to indicate that subjects with relapsed/refractory AML as well as subjects with MRD-positive AML will be evaluated in this trial
- Statistical considerations updated to account for MRD-positive AML subjects
- Schedule of assessments updated to include Day 8 assessments for Schedule C
- Schedule of assessments updated to include bone marrow assessments at safety follow-up and long-term follow-up visits where applicable
- Addition of extended intravenous (IV) and subcutaneous injection cohorts, using dose level review meeting (DLRM) approved doses
- Safety reporting language updated for adherence to current Amgen standard operating procedures (SOPs)
- References to Investigational Product Instruction Manual removed for adherence to current Amgen SOPs
- Update to References section
- Minor corrections and clarifications throughout

Amendment # 5

Protocol Title: A Phase 1 First-in-human Study Evaluating the Safety, Tolerability, Pharmacokinetics, Pharmacodynamics and Efficacy of AMG 427 in Subjects With Relapsed/Refractory Acute Myeloid Leukemia

Amgen Protocol Number AMG 427 20170528

IND number BB-IND 138440

NCT Number: NCT03541369

Eudra CT: 2018-001389-40

Amendment Date: 17 September 2020

